# Study Design:

Eighty breast cancer patients with Stage 0-III BrCA treated with breast conserving surgery or mastectomy and clear margins will be recruited to the study. Patients must have **one or more** of the following characteristics and be eligible for breast or chest wall with or without regional nodal radiotherapy:

1. Prior Chemotherapy for Breast Cancer

2. >25 cm of breast separation (the largest distance on an axial slice of the planning CT simulation scan between the entry and exit points of the radiation beam on the body)

- 3. Non-Caucasian Race
- 4. 4.
- 5. Requiring regional nodal irradiation without evidence of N3 disease

Because the above characteristics in isolation have been correlated with heightened levels of skin toxicity and/or were under-represented in previous trials of hypofractionated XRT, any patient fulfilling one of the above criteria, will be approached for enrollment in the study.

Males will be excluded.

To protect against possible side effects of radiation, women who are pregnant or nursing a child may not take part in this study.

Patients who have not received chemotherapy may start XRT up to 16 weeks after lumpectomy surgery. Patients who receive adjuvant chemotherapy after lumpectomy may start XRT up to 7 weeks after their last cycle of chemotherapy.

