Information regarding disease characteristics (including stage, tumor size, grade), patient demographics (including age, race, co-morbidities, social history, body mass index), systemic treatment (including hormone therapy, systemic therapy), surgical treatment, radiation treatment, and clinical outcomes (local control, distant metastasis, survival, and treatment complications) will be collected and recorded.

Patients may also be asked to participate in a long term assessment between 1 and 10 years where they will complete the same study procedures as outlined above. Patients will be compensated \$50.00 for completing this visit.

A follow up phone survey will be taken between 18 months and 10 years after treatment. Using the same scales as in the study visits, the patients will be asked to rate their fatigue level, breast pain, how happy they are with the look of their breast and how different their radiated breast is from their non-radiated breast. They will also be asked if they are on any hormonal treatment for breast cancer and if so, the date they started. We will obtain verbal consent for this survey from patients who completed this study before the follow up phone survey was originally approved on 9/24/2013.

Assuming 10% of patients dropout, 53 patients requiring breast only radiation will be enrolled (2-3 patients per month) to yield a total of 50 patients.

An additional 33 patients requiring regional nodal irradiation and breast or chest wall radiation will be enrolled. Assuming 10% of patients dropout, 33 patients of these patients will be enrolled (2-3 patients per month) to yield a total of 30 patients receiving regional nodal irradiation and breast or chest wall radiation.

In patients undergoing regional nodal irradiation, arm measurements will be taken of the ipsilateral and contralateral upper extremity at baseline, 7 - 12 weeks, and 12 – 18 months post XRT by a licensed lymphedema therapist or study staff trained by a licensed lymphedema therapist. These patients will also be assessed for brachial plexopathy using RTOG grading toxicity, LENT/SOMA grading toxicity, and a modified version of a validated questionnaire to assess symptoms of brachial plexopathy at baseline and 7 - 12 weeks, and 12 – 18 months post XRT.[24] If a patient develops RTOG or LENT/SOMA Grade 3 toxicity, an objective measurement (MRI and/or nerve conduction studies) of brachial plexopathy will be employed.

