### Monitoring Plan for Severe Adverse Events:

We hypothesize that a maximum of 20% of patients might experience severe acute skin side effects defined as NCI-CTC Grade 3. This corresponds to symptoms interfering with activities of daily life. A Data Safety and Monitoring Board (DSMB) will monitor patient outcomes and suspend the protocol in the event that more than 16 of 80 patients demonstrate severe acute skin toxicity. During the study, the patients will be monitored continuously throughout the study such that if at any time during the study the upper limit of the number of patients developing Grade 3 toxicity exceed what is listed in the table below, the trial will be discontinued. With a 10% dropout rate, a total sample size of 83 patients was calculated to effectively test our hypothesis. For patients not requiring regional nodal irradiation, we will only collect adverse events related to skin toxicity, lung toxicity and heart toxicity. We will not report grade 1-2 radiation dermatitis as adverse events because most patients will at least have gr 1 dermatitis. We will keep a record of toxicity at each visit by collecting the Lent Soma evaluation of

the clinician at each visit after treatment starts. Patient reported fatigue rate will not be collected on the adverse event report, but will also be recorded at each visit

Total Patients	Upper limit of number of patients with toxicity for the trial to continue	Proportion of patients with toxicity if exceed the upper limit	Lower limit of 95% Cl	Upper Limit of 95% CI
3	<3	100%	29%	100%
4	<4	100%	40%	100%
5	<4	80%	28%	99%
6	<4	67%	22%	96%
7	<5	71%	29%	96%
8	<5	63%	24%	91%
9	<5	56%	21%	86%
10	<6	60%	26%	88%
11	<6	55%	23%	93%
12	<6	50%	21%	79%
13-50	<7	>20%	NA	

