There is no drug in the proposed study. Our department has 7 linear accelerators all capable of delivering hypofractionated external beam radiotherapy. We also have extensive experience treating patients with simultaneous integrated boost radiotherapy. As determined by 2000 census, the majority of minorities in our community are African American, and African Americans make up 61.4% of the population of metropolitan Atlanta. A study including this population would be feasible. At the three Emory radiation centers, there are approximately 350 patients seen annually with 200 patients having early stage breast cancer. With approximately 80 African American breast cancer with Stage 0-II patients treated annually at Emory Clifton Campus, Emory Midtown, and Grady Memorial Hospital. In a recent study, over 60% of our patients had breast separation >25cm. [17] This trial should be able to accrue 33 high risk patients (2 to 3 patients per month, and assuming a 10% dropout rate) needed to assess the feasibility of this novel hypofractionated simultaneous integrated boost (SIB) regimen.

[name] (co-PI) is an NIH funded physicist with expertise in ultrasound tissue characterization (UTC) of radiation induced cutaneous toxicity. [name] Imaging Laboratory is fully equipped with three clinical ultrasound machines including a state-of-the art Sonix RP scanner with raw radiofrequency echo signals and advanced research interface. The laboratory is located on the tunnel level within the Department of Radiation Oncology. It comprises 500 sq. ft. and is equipped with ultrasound data acquisition system and calibration targets. UTC measurements will be easily performed in patients using [name] equipment and software. Measurements of breast tissue take about 10 minutes to complete.

The MFI, PSS, PSQI, IDS-SR, SF-36 and GLTEQ, and LENT SOMA are surveys which have been validated in various populations and take 15 minutes to complete in total.

Blood for inflammatory markers is routinely processed within the laboratory of my research mentor, [name], Professor of Psychiatry and an international expert on inflammatory induced behavioral changes. He has agreed to help process the blood from this study.

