**Data**

The SIB dataset was queried, and after exclusion and inclusion listed in the selection diagram file. Total 75 cases were included.

Selection and Exclusion Criteria	Sample Size	Excluded
SIB radiotherapy for breast cancer cases	75	-

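### The protocol gives two enrolment totals at the same 10% dropout, 83 and 53 + 33 = 86, and neither leaves the 80 patients it relies on

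*Protocol*

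**What the plan says.** Protocol, Monitoring Plan for Severe Adverse Events: "With a 10% dropout rate, a total sample size of 83 patients was calculated to effectively test our hypothesis". The same paragraph has the monitoring board "suspend the protocol in the event that more than 16 of 80 patients demonstrate severe acute skin toxicity".

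Protocol, Data Collection, assuming 10% dropout for each cohort:
- Breast only: "53 patients requiring breast only radiation will be enrolled (2-3 patients per month) to yield a total of 50 patients".
- Regional nodal: "An additional 33 patients requiring regional nodal irradiation and breast or chest wall radiation will be enrolled", and then "33 patients of these patients will be enrolled (2-3 patients per month) to yield a total of 30 patients".

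Two other places give a number for the whole study:
- The Study Design section opens with this: "Eighty breast cancer patients with Stage 0-III BrCA treated with breast conserving surgery or mastectomy and clear margins will be recruited to the study".
- The feasibility description: "This trial should be able to accrue 33 high risk patients (2 to 3 patients per month, and assuming a 10% dropout rate".

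The two stopping tables end at 50 patients (monitoring plan) and 30 patients (nodal section), which agrees with 50 + 30 = 80 as the evaluable base.

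**The concern.** Two sections of the current protocol apply the same dropout rate to the same study and reach different totals. The nodal patients are described as additional, so the 33 cannot be read as part of the 53. The 83 is presented as the result of a calculation, but the calculation is not shown, and 83 is not what the cohort sizes add up to.

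At stake is whether the plan has one enrolment figure and whether that figure supports the 80 used as the denominator of the overall skin-toxicity rule. Study Design says 80 will be recruited, although 80 matches the number expected after dropout. The feasibility description gives 33 as what the trial should accrue. A reader therefore meets 80, 83, 86 and 33, with nothing to say which is enrolled, which is evaluable and which is a subset.

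**Working it through.** **Inputs (all from the protocol).** Stated total 83 and dropout 10% (monitoring plan). Cohorts 53 to yield 50 and 33 to yield 30, dropout 10% (Data Collection). Denominator 80 (monitoring plan).

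**1. Can 83 be reproduced?**
- Sum of planned enrolment: 53 + 33 = 86. Sum of yields: 50 + 30 = 80.
- Inflating 80 by n/(1 − d): 80/0.9 = 88.9, so 89.
- Inflating 80 by n × (1 + d): 80 × 1.1 = 88.
- By cohort with n/(1 − d): 50/0.9 = 55.6, so 56; 30/0.9 = 33.3, so 34; total 90.

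None of 86, 88, 89 or 90 equals 83. A derivation from a hypothesis test cannot be tried: a 20% reference rate is given, but no alternative rate, alpha or power.

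**2. What does each total leave at 10% loss?**
- 83 × 0.9 = 74.7, which is 80 − 74.7 = 5.3 short of 80.
- 86 × 0.9 = 77.4 (53 × 0.9 = 47.7 plus 33 × 0.9 = 29.7), which is 80 − 77.4 = 2.6 short.

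**3. What dropout does each total imply if 80 remain?**
- 83 to 80: 3/83 = 3.6%.
- 86 to 80: 6/86 = 7.0%.

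**4. Which cohort departs from 10%?**

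| Cohort | Enrolled to yield | Implied loss | Needed at 10%: n × 1.1 | Needed at 10%: n/0.9, rounded up |
|---|---|---|---|---|
| Breast only | 53 to 50 | 3/53 = 5.7% | 55 | 56 |
| Nodal | 33 to 30 | 3/33 = 9.1% | 33 | 34 |

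The nodal figure is an ordinary 10% inflation. The breast-only figure is not.

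**5. Possible origins of 83.** 50 + 33 = 83, 53 + 30 = 83 and 75/0.9 = 83.3. All three come close, and the documents do not settle which, if any, was used.

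**6. Effect on the reported rate.** Sixteen events are 16/80 = 20.0%, 16/77 = 20.8% and 16/75 = 21.3%. Exact (Clopper-Pearson) 95% intervals near 20%:
- 16/80: 11.9% to 30.4%
- 15/77: 11.3% to 30.1%
- 15/75: 11.6% to 30.8%

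**The case against.** The strongest reply is that little turns on three patients. That is right about inference: the intervals in step 6 barely differ. The shortfalls of 5.3 and 2.6 are also upper limits, because acute skin toxicity is seen early and a patient lost later may still count for it. And if the stopping table that ends at 50 is read as the breast-only cohort's, the skin limit in the last row of each table is below 7. Stopping at 7 in each cohort gives 7 + 7 = 14 events, so the tables would act before the overall rule of more than 16. What remains is that a stated sample size disagrees with the protocol's own cohort sizes.

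A second reply is that 86 is no better as a 10% inflation of 80. That also stands. Replacing 83 by 86 alone would remove the contradiction but leave the 53 unexplained, so the yield or the dropout has to be restated with it.

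Three stronger readings are tempting and are not supported:
- That 83 arose because only the nodal cohort was inflated (50 + 33). Two other routes come as close, and the text supports none of them.
- That the 33 in the feasibility description is the nodal cohort. The number matches, but that sentence speaks of high-risk patients and does not mention nodal irradiation.
- That the SAP's count is wrong or shows a shortfall. The SAP says "Total 75 cases were included", which is a count of actual cases and need not equal a planned number. Its derivation may be in the selection diagram file that the SAP's Data section cites, which is not among the documents. That 83 less 10% is 74.7 may be coincidence.

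**Conclusion.** The inconsistency is real and minor. At the same 10% dropout the protocol gives 83 in one section and 86 by addition in another, a difference of 3, and the origin of 83 is not stated. On the assumption that dropouts are not evaluable, 83 leaves about 75 and 86 about 77, against a base of 80 that would need 88 to 90 enrolled. The 53 is the cohort figure out of line with 10%; the 33 is consistent with it. Precision is affected negligibly. The finding does not show that the trial was too small or that any toxicity conclusion would change.

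**What to change.** Wording changes to the protocol, with no added patients:

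1. Use one enrolment total in Data Collection and the monitoring plan. If the cohort sizes stand, it is 86. If 83 is the intended total, state how it was derived and correct the cohort sizes to match.
2. If 86 is kept, state with it either about 77 evaluable at 10% dropout (77.4 in total; about 48 breast-only and 30 nodal when each is rounded separately), or the dropout that 86 to 80 implies, roughly 7% overall and 5.7% in the breast-only cohort.
3. In Study Design, describe 80 as the evaluable target and not as the number recruited.
4. In the feasibility description, the sponsor should say what the 33 refers to.
5. The sponsor should reconcile the denominator of 80 in the suspension rule with the restated number. No new limit is proposed here.

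The cost is a few edited sentences and a slightly less favourable stated evaluable number or dropout assumption. As a side note only, if the SAP's selection diagram does not already trace the 75 cases back to the number enrolled, one line there would do so.

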Seeking to shorten the treatment course further and improve convenience and treatment adherence, we propose to build upon our experience and the level I evidence advocating for hypofractionation in 15 days of treatment. Our proposed study will utilize the SIB technique with the whole breast treated to 40 Gy in 15 fractions and the cavity boosted simultaneously to 48 Gy in 15 fractions. Only one previous study has examined the feasibility of a similar fractionation with the whole breast treated to 40.5 Gy in 15 fractions, while the cavity is treated to 48 Gy.(20) At 1 year median follow-up time, 67% of patients had developed reversible grade 1-2 skin dermatitis and only 1 of 91 patients had recurred locoregionally.(20) However, only 1/3 of patients received chemotherapy and less than a quarter had large breast size. The majority of patients were over the age of 50 and 87% were Caucasian.(20) No study has examined the feasibility of a 15-day hypofractionated SIB XRT regimen in women at high risk for cutaneous toxicity (e.g. women below the age of 50, African American, and/or treated with chemotherapy). The unique patient population served by Emory will enable a study of SIB XRT given 12/13/2016

over 15 treatments. Quality of life measures (e.g. Multidimensional Fatigue inventory (MFI)[18], the Pittsburgh Sleep Quality Index (PSQI) [19], the perceived stress scale (PSS)[20], the Inventory of Depressive Symptomalogy-Self Reported (IDS-SR)[21], the Short-Form Health Survey (SF-36)(25) and the Godin Leisure Time Questionnaire (GLTEQ)(26)) which have been validated in multiple populations, will also be assessed in these patients to determine if 15 days of treatment is feasible.

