### Data Collection:

Cutaneous toxicity will be assessed at baseline, fraction 15 of XRT and 2 - 5 weeks, 7 - 12 weeks, and 12 – 18 months post XRT by objective ultrasound measurements (UTC). Photographs of the treated breast or chest wall as well as the contralateral breast will also be taken. Documentation of the UTC and photographs will be kept in electronic format for reference. For each visit after the baseline (after treatment has begun), cutaneous toxicity will be assessed by a clinician. Participants will be seen by the investigator in follow up at the third and/or fourth visits and at the fifth visit and an investigator dictation will be performed.

Patients who have had a mastectomy and plan for permanent breast reconstructive surgery after radiation will be assessed within one month of their permanent reconstructive surgery and 5 - 7 months following their surgery using the same procedures as described above. It is highly variable as to when reconstruction will occur. If these time points do not fall within the time frame for the regular study visits, additional study visits will be added for these patients.

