#### **Objectives:**

**Primary objective:** To assess the safety and feasibility of delivering 15 fractions of SIB radiotherapy to the breast in patients at risk for developing cutaneous toxicity.

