will be monitored throughout the study such that if at any time during the study the upper limit of the number of patients receiving regional nodal irradiation developing Grade 3 brachial plexopathy or 20% or greater increase in arm lymphedema exceed the number just described or more than 20% develop grade 3 skin toxicity within the breast or chest wall, the trial will be discontinued to the patients requiring regional nodal irradiation but may remain open to patients who do not require regional nodal irradiation. For patients requiring regional nodal irradiation, we will only collect adverse events related to brachial plexopathy, lymphedema, skin toxicity, lung toxicity, heart toxicity. We will not report grade 1-2 radiation dermatitis as adverse events because most patients will at least have gr 1 dermatitis. We will keep a record of toxicity at each visit by collecting the Lent Soma evaluation of the clinician at each visit after treatment starts. Patient reported fatigue rate will not be collected on the adverse event report, but will also be recorded at each visit.

Stopping rule for monitoring 3 types of toxicities in patients Receiving Regional Nodal Irradiation.

Total Patients	Upper limit of number of patients with Grade 3 brachial plexopathy (<3%)	Upper limit of number of patients with 20% or greater increase in arm lymphedema (<15%)	Upper limit of number of patients with grade 3 skin toxicity within the breast or chest wall (<20%)
3	<2	<3	<3
4	<2	<3	<4
5	<2	<4	<4
6	<2	<4	<4
7	<2	<4	<5
8	<2	<4	<5
9	<2	<5	<5
10	<2	<5	<6
11	<2	<5	<6
12	<2	<5	<6
13-30	<2	<5	<7

(If any one of the 3 stopping rules is met, the trial stops for excessive toxicity.)

**Correlative Studies**: Blood will be analyzed for inflammatory markers (TNF-alpha, soluble sTNFR2, IL-6, IL-1ra, and CRP) to determine if they are associated with development of cutaneous toxicity. By acquiring the objective UTC measurements at 5 time points, the development and resolution of cutaneous toxicity as it relates to time may be further understood.

A description of the Feasibility:

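### Adverse event collection is closed to three or five listed categories, so a serious event outside the list does not enter the adverse event record although safety is the primary objective

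*Protocol*

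**What the plan says.** The primary objective in the protocol (Objectives) is "To assess the safety and feasibility of delivering 15 fractions of SIB radiotherapy to the breast" in patients at risk of cutaneous toxicity. Background states that "No study has examined the feasibility of a 15-day hypofractionated SIB XRT regimen in women at high risk for cutaneous toxicity", and the description of feasibility calls the regimen novel.

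The rule on adverse events appears twice, once for each patient group:

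- Monitoring Plan for Severe Adverse Events, patients not requiring nodal irradiation: "we will only collect adverse events related to skin toxicity, lung toxicity and heart toxicity".
- Patients Requiring Regional Nodal Irradiation: "we will only collect adverse events related to brachial plexopathy, lymphedema, skin toxicity, lung toxicity, heart toxicity".

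Both sections also exempt low-grade dermatitis: "We will not report grade 1-2 radiation dermatitis as adverse events because most patients will at least have gr 1 dermatitis". Both keep a clinician LENT SOMA evaluation at each visit after treatment starts.

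Two items in Data Collection bear on the same events. The first provides extra visits: "Patients who have had a mastectomy and plan for permanent breast reconstructive surgery after radiation will be assessed", once within a month of that surgery and once 5 to 7 months after it, using the ordinary study procedures. The second is a general data item: "clinical outcomes (local control, distant metastasis, survival, and treatment complications) will be collected and recorded".

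The SAP lists skin thickening ratio, overall survival, and local and distant recurrence-free survival as outcomes. It gives a three-level toxicity scale, but no analysis of adverse events.

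**The concern.** A closed list can measure only the harms that were foreseen. That is reasonable when a treatment's harms are well known in the population treated. Here the protocol itself says that the evidence is thin: the one similar study that it describes had 91 patients with a median follow-up of 1 year, and Background says that post-mastectomy patients and patients needing nodal irradiation were under-represented in the UK START study.

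If an event outside the list is not an adverse event for trial purposes, its absence from the adverse event table says nothing about whether it happened. The final safety statement could then look favourable partly because of how events were ascertained. The monitoring board would also have no defined route by which to learn of such an event.

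**Working it through.** The plan states no figure on this point, so there is none to reproduce. The check is mainly a comparison of the text, followed by a short illustration of scale.

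**Step 1: is the list really closed?** Both sentences use the word only. Neither list has an entry for other or unexpected events. The section is titled for severe adverse events, but no supplied text defines a serious adverse event or gives a reporting rule for one. On its wording, the list is closed.

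**Step 2: what falls outside it?** An event of the skin, lung or heart is inside both lists. Brachial plexopathy and lymphedema are inside the nodal list. Outside both are, for example, a reconstruction complication that does not involve the skin, or a serious event in another organ. The contralateral breast has a dose limit under Dose Constraints to Normal Tissues but appears in neither list.

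**Step 3: which list applies to reconstruction patients?** The enrolment plan in Data Collection has 53 patients for breast-only radiation and 33 for nodal irradiation with breast or chest wall radiation. On that plan, chest wall patients sit in the nodal group, so mainly the five-category list applies to them. Study Design is wider and admits chest wall treatment without nodal irradiation; such a patient would come under the three-category list. No reconstruction complication is named in either list or as an outcome.

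**Step 4: is there another route?**

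| Route | What it captures | Link to adverse event report or board |
|---|---|---|
| Treatment complications (Data Collection) | Any complication, with no organ limit | None stated; no definition, grade or timing |
| Clinician LENT SOMA at visits | Items on a structured toxicity scale | Kept as a record of toxicity; not described as a route for other serious events |
| Reconstruction visits | Ordinary study procedures | None stated |
| Monitoring board | Patient outcomes in general | All stated triggers concern skin toxicity, brachial plexopathy or lymphedema |

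The monitoring plan itself treats recording and adverse event reporting as separate: patient-reported fatigue is left off the adverse event report but is recorded at each visit. An event that is recorded somewhere is therefore not thereby in the adverse event record.

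**Step 5: illustration of scale.** The true rate p of an unlisted harm is an assumption; the documents give none. The numbers of patients n are 80 (Study Design), 75 (SAP, Data) and 30 (target number of nodal patients, Data Collection).

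- Chance of at least one event: 1 − (1 − p)^n. Expected events: n × p.
- n = 80, p = 1%: 1 − 0.99^80 = 0.552; expected 0.8.
- n = 80, p = 2%: 1 − 0.98^80 = 0.801; expected 1.6.
- n = 80, p = 5%: 1 − 0.95^80 = 0.983; expected 4.0.
- n = 75, p = 2% and 5%: 0.780 and 0.979.
- n = 30, p = 2% and 5%: 0.455 and 0.785.

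If all such events were collected and none were seen, the exact one-sided 95% upper bound on the rate would be 1 − 0.05^(1/n): 3.7% for n = 80, 3.9% for n = 75 and 9.5% for n = 30. Under the closed list, zero entries in the adverse event record support no bound for an unlisted event type.

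**The case against.** The strongest reply is that the information is not lost. Data Collection records treatment complications, survival, distant metastasis and surgical treatment with no organ limit. Clinicians complete LENT SOMA at each visit after treatment starts. The reconstruction visits repeat the usual assessments, and the board is to monitor patient outcomes without being confined to adverse event forms. Targeted collection is also a legitimate choice for expected low-grade events.

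Much of this stands, and it rules out three stronger readings that a reader might infer:

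- *That unlisted events are never collected.* The documents do not support this. Such an event may well be in the dataset as a treatment complication; it is only kept out of the adverse event record.
- *That the two sections contradict each other.* They can both be followed, because one governs data collection and the other adverse event reporting. The defect is that nothing connects them.
- *That the board can see only the listed categories.* The protocol does not say so. It says only that the stated triggers concern listed toxicities.

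The absence of lymphedema and plexopathy from the breast-only list is also a weak complaint. The protocol prescribes nodal treatment only for patients requiring it and confines both outcomes to that group, so leaving them out is a defensible choice.

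Finally, a serious-event rule may exist in removed pages or in institutional policy. That limits certainty, but the supplied text refers to none, and the word only would have to be reconciled with it.

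What the reply does not answer is that a complication with no definition, grade, timing or route to the board cannot stand in for safety reporting.

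**Conclusion.** The point holds in a limited form. In both groups the adverse event list is closed by its own wording, and a serious or Grade 3 or higher event outside it does not enter the adverse event record of a trial whose primary objective includes safety. The fallback record of treatment complications is ungraded, undefined and not tied to the adverse event report or to any stated trigger.

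The restriction applies to both groups, but the reconstruction example concerns mainly the chest wall patients within the 33 planned for nodal irradiation. The size cannot be derived from the documents. The 80% and 98% figures for 80 patients rest on assumed true rates of 2% and 5%, and show only that a harm of that frequency would probably occur at least once. The conclusion also assumes that no serious-event rule exists outside the supplied text.

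**What to change.** In both sentences that restrict collection, replace the restriction with the listed categories plus every serious adverse event and every Grade 3 or higher event judged at least possibly related to radiotherapy, whatever the organ. Say explicitly that complications seen at the reconstruction visits are included. Keep the exemption for Grade 1–2 dermatitis. State that these events, together with the treatment complications recorded under Data Collection, go to the monitoring board. If a serious-event rule already applies from elsewhere, cite it and align the wording.

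The SAP, dated 04/01/2021, describes the study in the past tense and reports 75 cases, so an amendment may come too late for some or all patients. Where collection is complete, grade and tabulate the recorded treatment complications. State in any safety conclusion that adverse event ascertainment was restricted to the listed categories.

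The cost is a few more forms, drawn largely from visits and records already planned, and some attribution work for the investigator. Retrospective grading will be less reliable than prospective grading, and the report should say so.
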